13.6.2. Clinical Laboratory Evaluations

Results of clinical laboratory parameters in each scheduled visit and mean changes from baseline will be summarized in standard units. Normal ranges for each parameter will be provided by the laboratory; shift from baseline to postbaseline values in abnormality of results will be provided. Potentially clinically significant values will be summarized by treatment. Clinical laboratory results will be listed by participant and timing of collection.

13.6.3. Physical Examinations

The occurrence of a physical examination (yes/no) and the date performed will be listed by participant.

13.6.4. Vital Signs

Vital sign results at each visit and mean changes from baseline will be summarized by scheduled visit. Potentially clinically significant values will be summarized by treatment. Vital sign results will be listed by participant and timing of collection.

13.6.5. 12-Lead Electrocardiogram

The following ECG parameters will be listed for ECGs for each participant: heart rate, PR, QRS, QT, and QTcF. ECG data will be summarized by visit. Potentially clinically significant values of QTcF will be summarized by treatment. ECG findings will be listed by participant and visit.

13.6.6. Prior and Concomitant Medications

Medications will be recorded at each study visit during the study and will be coded using World Health Organization-Drug Dictionary September 2015, or later.

All medications taken within 30 days prior to signing the informed consent through the duration of the study will be recorded. In addition, all psychotropic medications taken in the previous 30 days prior to Screening will be recorded. All medications taken at any time prior to signing the informed consent through the duration of the study for ET will also be recorded. Those medications taken prior to the initiation of the start of IP will be denoted "Prior". Those medications taken prior to the initiation of the IP and continuing beyond the initiation of the IP or those medications started at the same time or after the initiation of the IP will be denoted "Concomitant".

Medications will be presented according to whether they are "Prior" or "Concomitant" as defined above. If medication dates are incomplete and it is not clear whether the medication was concomitant, it will be assumed to be concomitant.

Details of prior and concomitant medications will be listed by participant, start date, and verbatim term.

13.8. Sample Size and Power

The planned sample size is 160 participants, randomized in a 1:1:1:1 ratio to each of the dose group (placebo and SAGE-324: 15 mg, 30 mg, and 60 mg), stratified by baseline propranolol use, with at least 104 (65%, 26 participants per dose group) monotherapy participants and up to 56 (35%, 14 participants per dose group) adjunct therapy participants.

The sample size of 104 participants for the monotherapy cohort assumes a change from baseline at Day 91 in TETRAS upper limb Item 4 score for the placebo group of -1.2 points, a maximum decrease of -3.2 points from Baseline for a dose response in the 15-60-mg dose groups with a standard deviation of 2.5. Under these assumptions with a few prespecified candidate dose-response models, including linear, loglinear, quadratic, exponential, logistic, Emax, sigEmax, and beta as shown in Figure 3, a sample size of 22 evaluable participants per group would provide 80% power for demonstrating a nonflat dose-response relationship by MCP-Mod approach, using a 1-sided type I error rate of 0.05. Assuming a nonevaluable rate of 15% across all treatment groups, approximately 104 participants (26 per treatment group) will be

randomized. Additional participants may be enrolled if the overall nonevaluable rate is higher than 20%.

The sample size for adjunct therapy cohort is not based on statistical significance, but clinical considerations. Up to 56 adjunct therapy participants (14 per dose group) are to provide some adjunct therapy directional data on both efficacy and safety measures.

A blinded interim look at the primary and secondary endpoint data may be conducted to evaluate the sample size assumptions.

Additional participants may be randomized if the variances are larger than the assumptions above. However, no more than 200 participants, including adjunct therapy participants, will be randomized.

Figure 3: Prespecified Dose-response Models

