7.2. Number of Participants

Approximately 160 participants, with at least 104 (65%, 26 participants per dose group) monotherapy participants and up to 56 (35%, 14 participants per dose group) adjunct therapy participants, will be randomized to ensure at least 22 participants per arm in the monotherapy cohort will complete the study.

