8.4.4. Replacement of Participants

Participants will not be replaced.

Additional monotherapy participants may be enrolled at the discretion of the sponsor to achieve at least 22 evaluable participants per dose group.

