9.5. Randomization and Blinding

This is a randomized, double-blind, placebo-controlled study. Participants will be randomized in a 1:1:1:1 ratio to treatment groups (15 mg, 30 mg, 60 mg SAGE-324, or placebo) stratified by baseline propranolol use (adjunct therapy). Participants, site staff, and the sponsor will be blinded to treatment allocation (see study schematic in Figure 2).

Randomization schedules will be generated by an independent statistician. The randomization schedules will be kept strictly confidential, accessible only to authorized personnel until the time of unblinding. The blinding of the study will be broken after the database has been locked.

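### The 20% top-up trigger protects about 20.8 evaluable participants per arm, not the 22 on which the stated power rests, and 26 per arm does not ensure 22

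*Protocol*

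**What the plan says.** Protocol 13.8 gives the basis of the size: "a sample size of 22 evaluable participants per group would provide 80% power for demonstrating a nonflat dose-response relationship by MCP-Mod approach". The test is one-sided at the 0.05 level. The section allows for 15% nonevaluable and arrives at 26 per group, 104 in all. It then adds: "Additional participants may be enrolled if the overall nonevaluable rate is higher than 20" per cent. SAP 5.2 repeats this. The Synopsis has the same 20% threshold but limits the added participants to monotherapy.

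Two other places in the protocol bear on the same number:

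- Section 7.2, and the Synopsis in the same terms, say the participants are randomised "to ensure at least 22 participants per arm in the monotherapy cohort will complete the study".
- Section 8.4.4 lets the sponsor, at its discretion, enrol more monotherapy participants "to achieve at least 22 evaluable participants per dose group". It gives no rate threshold.

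On who could count by arm, Protocol 9.5 says "Participants, site staff, and the sponsor will be blinded to treatment allocation". It restricts the randomisation schedules to authorised personnel, whom it does not name. SAP 9.2 lists no data monitoring committee analysis.

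**The concern.** The allowance for losses and the safeguard against excess losses are set at different rates. The first is 15%, the second 20%. Between them lies a band of outcomes in which the evaluable number is below the one behind the power statement and the stated trigger stays silent.

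The section that does name 22 per dose group as a target is optional. It is not cross-referenced to the 20% rule, and it needs a count by arm for which no procedure is given. Meanwhile 7.2 promises 22 in every arm, although 22.1 is only the expected count. At stake is whether the size the plan says it protects is the size it does protect.

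**Working it through.** **Inputs.** From Protocol 13.8: 22 evaluable per group, 15% nonevaluable, 26 per group, 104 in total, 20% trigger, one-sided 0.05, change from baseline "for the placebo group of -1.2 points, a maximum decrease of -3.2 points from Baseline" (maximum difference 2.0), "with a standard deviation of 2.5". The candidate shapes come from the code in SAP 8.3.3.1. I read the overall rate as the rate across the four monotherapy arms.

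**1. The plan's own size.** 22 / 0.85 = 25.9, rounded up to 26 per group; 4 x 26 = 104. Expected evaluable: 26 x 0.85 = 22.1. This reproduces.

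**2. What each rate leaves.**
- Largest loss that keeps 22 of 26: 1 - 22/26 = 15.4%.
- At the trigger: 26 x 0.80 = 20.8 per arm (104 x 0.80 = 83.2 in total).

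**3. In whole participants, at exactly 104 randomised.**

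| Losses | Rate | Evaluable | Mean per arm | Above 20%? |
|---|---|---|---|---|
| 16 | 15.4% | 88 | 22.00 | no |
| 17 | 16.3% | 87 | 21.75 | no |
| 18 | 17.3% | 86 | 21.50 | no |
| 19 | 18.3% | 85 | 21.25 | no |
| 20 | 19.2% | 84 | 21.00 | no |
| 21 | 20.2% | 83 | 20.75 | yes |

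The gap is 17 to 20 losses.

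**4. How often the gap would occur.** Assume each participant is independently nonevaluable at a common rate. With E ~ Binomial(104, 1 - rate), P(84 ≤ E ≤ 87) is 0.30 at a true rate of 15%, 0.39 at 18% and 0.34 at 20%.

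**5. Does 26 ensure 22?** Same assumption, with X ~ Binomial(26, 1 - rate) in each arm:
- Rate 15%: P(X ≥ 22) = 0.650; all four arms 0.650^4 = 0.18.
- Rate 20%: P(X ≥ 22) = 0.383; all four arms 0.383^4 = 0.02.

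**6. Power.** I simulated the maximum contrast statistic (300,000 draws, optimal contrasts at doses 0, 15, 30 and 60, maximum effect 2.0, SD 2.5, one-sided 0.05, t reference). The SAP code passes no log offset and no beta scale to the model-set call. I assumed an offset of 0.6 and ran the scale at 72, and at 65, the value used in the SAP's beta guesstimate.

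| Per arm | Scale 72: minimum / mean over 8 models | Scale 65: minimum / mean |
|---|---|---|
| 22 | 79.2% / 84.4% | 65.6% / 82.3% |
| 20.8 | 77.2% / 82.5% | 63.4% / 80.4% |

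The stated 80% reproduces as the minimum over the models at scale 72 (79.2% with a t reference, 80.0% with a normal reference). Moving from 22 to 20.8 costs about 2 points under either scale. The beta model is the minimum in every row, and its level depends mainly on the scale.

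**The case against.** Four points can be made for the plan as written.

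- **Section 8.4.4 already covers the gap.** This stands. It has no rate threshold, and the 20% sentence is itself permissive and forbids nothing below 20%. A reader might infer that losses between 15.4% and 20% must go without action; the documents do not say so. What remains is that neither rule is required and neither refers to the other.
- **A per-arm count is not impossible.** A reader might infer that a blinded sponsor cannot operate 8.4.4 at all. The documents do not support that. Authorised personnel holding the schedules could report a count, and under 1:1:1:1 allocation the sponsor can work to a pooled total while blinded. What is missing is a stated procedure.
- **104 is a floor.** The plan says at least 104 monotherapy participants and up to 56 adjunct. If fewer adjunct participants enrol and the total of 160 is kept, monotherapy exceeds 104 and the gap narrows or closes. The whole-participant and binomial figures hold at exactly 104.
- **A margin between planning rate and trigger is a legitimate choice, and little power is lost.** Both stand. The mixed model on the Full Analysis Set also uses partial data from participants without a Day 91 score. A reader might read the 63% to 66% beta figures as the price of the trigger; they come from the assumed scale, and the trigger accounts for only about 2 points. A deliberate margin should still be stated with the size it protects.

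**Conclusion.** The inconsistency is real and of low consequence. The 20% trigger protects about 20.8 per arm (21.0 in the worst untriggered whole-number case at 104), while the power statement rests on 22. The claim in 7.2 and the Synopsis that 22 per arm is ensured is not supported by the plan's own rate: all four arms reach it with probability about 0.18 at 15% and 0.02 at 20%. The two top-up rules do not contradict each other, but they are unlinked, and the per-arm one has no operating procedure. The power cost is about 2 points.

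The probabilities assume independent losses at one common rate and exactly 104 randomised. They also treat evaluable as a single yes/no status, which the documents never define; 7.2 counts completers instead, and 7.6 takes completion through the Day 104 visit. The power levels rest on the assumed offset and beta scale; the 2-point difference hardly depends on the scale.

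**What to change.** 1. In Protocol 7.2 and the Synopsis, replace the statement that 22 per arm is ensured with: *so that about 22 per arm are expected at a 15% nonevaluable rate*.
2. In Protocol 13.8, the Synopsis and SAP 5.2, do one of the following:
   - keep the 20% trigger and state that it protects about 20.8 per arm, with the power at that size; or
   - replace it with one blinded pooled rule consistent with 8.4.4: *additional monotherapy participants may be enrolled if fewer than 88 evaluable monotherapy participants in total are projected*.

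If the second option is taken, use the count and not a 15% rate. At 16 losses of 104 the rate is 15.4%, above 15%, yet exactly 88 remain, so the two wordings would give opposite answers. Whichever option is chosen, define evaluable once and have 8.4.4 refer to the same rule. If a count by arm is wanted, name who makes it.

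**Cost.** The first option costs wording and a slightly less favourable stated figure. The second costs about 6 more monotherapy participants in expectation at a 20% rate (88 / 0.80 = 110, against 104). With 56 adjunct participants that makes 166, inside the cap of 200. A pooled 88 gives 22 per arm on average and does not guarantee it in each arm. Randomising 110 at a 20% rate reaches 88 with probability about 0.56. The rule should stay permissive; nothing here justifies making added enrolment mandatory.

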13.8.1. Interim and Data Monitoring Committee Analyses

A blinded interim look at the primary and secondary endpoint data may be conducted to evaluate the sample size assumptions.

14. DIRECT ACCESS TO SOURCE DATA/DOCUMENTS

14.1. Study Monitoring

Unless otherwise waived or addressed in another forum (eg, investigator meeting), before an investigational site can enter a participant into the study, a representative of Sage will visit the investigational study site to:

- Confirm the adequacy of the facilities
- Discuss with the investigator(s) and other personnel their responsibilities with regard to protocol adherence, IP management, GCP/ICH GCP compliance, and the responsibilities of Sage or its representatives. This will be documented in a Clinical Trial Agreement between Sage and the investigator.

During the study, a monitor from Sage or representative will have regular contacts with the investigational site, for the following:

- Provide information and support to the investigator(s)
- Confirm that facilities remain acceptable
- Confirm that the investigational team is adhering to the protocol, that data are being accurately recorded in the eCRFs, and that IP accountability checks are being performed
- Perform source data verification. This includes a comparison of the data in the CRF with the participant's medical records at the hospital or practice, and other records relevant to the study. This will require direct access to all original records for each participant (eg, medical records, source documents, clinic charts)
- Record and report any protocol deviations not previously sent to Sage Therapeutics
- Confirm AEs and SAEs have been properly documented on eCRFs and confirm any SAEs have been forwarded to Sage Therapeutics and those SAEs that met criteria for reporting have been forwarded to the IRB or IEC.

The monitor will be available between visits if the investigator(s) or other staff needs information or advice.

14.2. Audits and Inspections

Sage Therapeutics or authorized representatives of Sage Therapeutics, a regulatory authority, or an IRB/IEC may visit the site to perform an audit(s) or inspection(s), including source data verification. The purpose of a Sage Therapeutics audit or a regulatory authority inspection is to systematically and independently examine all study-related activities and documents to determine whether these activities were conducted, and data were recorded, analyzed, and accurately reported according to the protocol, Good Clinical Practice (GCP)/International Council for Harmonisation (ICH) guidelines, and any applicable regulatory requirements. The investigator should contact Sage Therapeutics immediately if contacted by a regulatory agency or IRB/IEC about an inspection.

14.3. Institutional Review Board or Independent Ethics Committee

The principal investigator must obtain IRB (or IEC) approval for the clinical study prior to enrolling a participant. Initial IRB (or IEC) approval, and all materials approved by the IRB (or IEC) for this study including the participant consent form and recruitment materials must be maintained by the investigator and made available for inspection.

15. QUALITY CONTROL AND QUALITY ASSURANCE

To ensure compliance with GCP and all applicable regulatory requirements, Sage Therapeutics may conduct a quality assurance audit(s) at the clinical site. Please see Section 14.2 for more details regarding the audit process.

The investigator must have adequate quality control practices to ensure that the study is performed in a manner consistent with the protocol, GCP/ICH GCP guidelines, and applicable regulatory requirements. The investigator is responsible for reviewing all identified protocol deviations. Protocol deviations that harm or increase the possibility of harm to the rights and welfare of a participant or a deviation made without prior IRB/IEC approval to eliminate an immediate hazard to the participant should be reported to the IRB/IEC per the IRB/IEC's written procedures.

The investigator is responsible for supervising any individual or party to whom the investigator delegates study-related duties and functions conducted at the study site. When the investigator retains the services of any individual or party to perform study-related duties and functions, the investigator must ensure the individual or party is qualified to perform study-related duties and functions and should implement procedures to ensure the integrity of the study-related duties and functions performed, and any data generated.

The investigator must maintain adequate and accurate source documents and study records that include all pertinent observations on each of the site's study participants. Source data must be attributable, legible, contemporaneous, original, accurate, and complete. Changes to source data should be traceable, should not obscure the original entry, and should be explained, if necessary to provide clarification.

16. ETHICS

16.1. Ethics Review

The final study protocol, including the final version of the ICF, must be given a written and dated approval or favorable opinion by an IRB/IEC, as appropriate. The investigator must obtain and document approval before he or she can enroll any participant into the study. The IRB/IEC must supply to the sponsor a list of the IRB/IEC membership and a statement to confirm that the IRB is organized and operates according to GCP and applicable laws and regulations.

The principal investigator is responsible for informing the IRB/IEC of any amendment to the protocol in accordance with local requirements. In addition, the IRB/IEC must approve all advertising used to recruit participants for the study. The protocol must be re-approved by the IRB or IEC upon receipt of amendments and annually, as local regulations require.

The principal investigator is also responsible for providing the IRB/IEC with reports of any reportable serious adverse drug reactions from any other study conducted with the IP. Sage Therapeutics will provide this information to the principal investigator.

Progress reports and notifications of serious adverse drug reactions will be provided to the IRB/IEC according to local regulations and guidelines. In addition, the principal investigator must inform the IRB/IEC and sponsor of any changes significantly affecting the conduct of the study and/or increasing the risk to participants (eg, violations to the protocol or urgent safety measures taken for participant safety).

16.2. Ethical Conduct of the Study

The study will be performed in accordance with ethical principles that have their origin in the Declaration of Helsinki and are consistent with ICH and GCP guidelines, as well as all applicable regional or national regulatory requirements.

16.3. Written Informed Consent

Prior to enrolling a study participant, the investigator(s) will ensure that the participant is given full and adequate oral and written information about the nature, purpose, possible risk, and benefit of the study. Participants must also be notified that they are free to discontinue from the study at any time. The participant should be given the opportunity to ask questions and allowed time to consider the information provided.

When the participant decides to participate in the study, the participant (or the participant's parent or legally authorized representative) must provide signed and dated informed consent. The written consent must be obtained before conducting any study procedures. The investigator must document the consent process in the participant's source documentation. The investigator must maintain the original, signed ICF. A copy of the signed ICF must be given to the participant or to the participant's parent or legally authorized representative.

The ICF will include a provision stating that the participant may be contacted during or after the study with a request to participate in a related, follow-up research study in which they will be asked to provide responses to various questions regarding their experience in the Phase 2 study.

Throughout the study participants should be informed of any changes made to the study and as new safety and or risk information becomes known. The provision of this information will be documented in the participant's source records, and when applicable, an updated ICF will be provided.

16.4. Data Protection

- Participants will be assigned a unique identifier by the sponsor. Any participant records or datasets that are transferred to the sponsor will contain the identifier only; participant names or any information which would make the participant identifiable will not be transferred.
- The participant must be informed that his/her personal study-related data (including but not limited to, retained biological samples, images and/or recordings) will be used by the sponsor in accordance with local data protection law. The level of disclosure must also be explained to the participant who will be required to give consent for their data to be used as described in the informed consent.
- The participant must be informed that his/her medical records may be examined by Sage Quality Assurance auditors or other authorized personnel appointed by the sponsor, by appropriate IRB/IEC members, and by inspectors from regulatory authorities.

17. DATA HANDLING AND RECORDKEEPING

17.1. Inspection of Records

Sage Therapeutics or its representative(s) will be allowed to conduct visits at the investigation site and/or supporting facilities for the purpose of monitoring any aspect of the study. The investigator agrees to allow the monitor to inspect the facility, drug storage area, drug accountability records, participant medical records and study source documents, and other records relative to study conduct.

Inspection of the study by a regulatory authority may occur at any time. The investigator must agree to the inspection of study-related records and source documents by the regulatory authority representative(s).

